**Study Population:**

In the intervention study arm, we will enroll up to 431 individuals and 400 historical control group participants.

**Inclusion/exclusion criteria for intervention study arm.** In this study, the inclusion criteria for the enrolled intervention study arm individuals include being aged 18 years to 89 years and having a smartphone that accepts text messages. The exclusion criteria will include: (1) having been diagnosed with COVID-19 in the past 30 days based on a positive test (antigen or PCR) or a clinical diagnosis, (2) having tested for COVID-19 with PCR or antigen test within the past 30 days, (3) not being available in the recruitment area in the next 60 days, (4) having been an embedded study participant and (5) having been a snowball study participant.

**Selection of the study population.** Three large regions of Texas: 1) Houston/Harris County; 2) Cameron County in South Texas; and 3) seven counties, including the city of Tyler in Northeast Texas. The communities prioritized in this proposal include populations with medical comorbidities, and underserved Hispanics and African Americans in three racially diverse regions: South Texas, Houston/Harris County, and Northeast Texas.

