## Summary of Embedded Study Survey Constructs

Measures / Constructs	Questions	Citation/Tool
Testing behavior	Testing for COVID-19, ever tested, last 30 days, positivity, access to testing	Funder required items, Novel items
COVID-19 history	COVID-19 sickness, hospitalization (self or others)	Funder required items, Novel items
Intention to test	Likelihood of testing (ever, 30 days), intention to test as needed	Funder required items, Novel items
Self-efficacy to test	Certainty of ability to be tested given situational contexts	Adapted self-efficacy measures following Maibach (1995) 
Pandemic safety behaviors	Wearing masks in private settings, wearing masks in public settings, washing/sanitizing hands, intentional social distancing (Never, some of the time, very often, all of the time)	Adapted for CEAL Program from Center for Economic and Social Research Understanding America Study Coronavirus Tracking Survey. https://www.phenxtoolkit.org/covid19/source
Vaccination	Vaccine uptake, type, doses	Funder required items
Trusted Sources of Information	Sources of information (doctor, media, health department, etc)	Funder required items
COVID-19 Perceived Susceptibility/Severity	How concerned are you about contracting COVID-19? How likely is it that you will get COVID-19?	Savoia E. et al, 2021 

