- 3) **Missing data:** The enrolled individuals completing the follow-up survey constitute the analysis set. Every effort will be made to keep all participants in the study and to obtain required data at each scheduled time point. All information for patients who dropped out from the study will be recorded and stored in the database. Traditional regression techniques usually assume that all data are complete and will produce unbiased estimates and valid inferences under missing completely at random (MCAR) assumption. We will examine drop-outs, missing data and measurement errors which are common problems with longitudinal data structure to be able to identify accurate missing data mechanisms and patterns so that we can explain missing data mechanism. If the missing data are non-ignorable/informative in the sense that missingness may depend on the missing observations, modeling of the informative missing data or dropout processes will be conducted. An attempt will be made to incorporate the missing values mechanism into the model as discussed in Little and Rubin. All Analyses will be performed primarily using widely available tools in SAS® version 9.4 (SAS Institute, Cary, NC) or R, at a significance level of 0.05.
- 4) **Quality Assurance (QA) & Quality Control (QC) Procedure** Upon completion of resolving data cleaning, the data quality control process will be initiated. The QC process involves 1) randomly selected patients (10-20%), 2) comparing source documents to CRFs, and 3) comparing CRFs with the database. In all processes, we will select critical variables that determine the safety/effectiveness of what will be used in statistical analysis.

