## Statistics

**Statistical Analysis - Main Study Primary Outcomes.** We will conduct a series of analyses regarding the primary outcome variable - testing for COVID-19. First, we will conduct McNemar's test on data from the prospective cohort only. In addition to the test p-value, the odds ratio of COVID-19 testing for post-intervention versus baseline will be evaluated to assess the intervention effect. Second, based on both the prospective cohort and historical controls, we will find inferences for the ratio of odds ratios for intervention versus control. Third, using the prospective cohort, we will build a multi-level generalized linear mixed model (GLMM) including time as a fixed effect factor to evaluate intervention effect. Multiple random effects will be specified to account for the hierarchical structure of persons nested within PBGs nested within regions. Additionally, we will test variables such as individual demographics and baseline measures of rapid testing uses and include significant variables as the fixed effect factors. We will also test the PBG-level of Social Determinants of Health (SDOH) (e.g., % of minority, % of people with no insurance) to investigate the SDOHs as a potential effect modifier on the intervention effectiveness. We will also compute various network measures based on personal networks and organization affiliation patterns associated with COVID-19-related outcomes. Finally, we will build a GLMM to data of both the prospective cohort and historical controls. We will specify proper random effects to account for hierarchical nesting structure.

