### Sample Size for Testing the primary hypothesis in this study.

We have estimated the sample size of the prospective cohort based on the primary hypothesis that individuals experiencing the intervention of Phase III will have higher levels of effective use of SARS-CoV-2 testing than their testing at baseline. The McNemar test, together with the odds ratio (OR) of COVID-19 testing for post-intervention versus baseline, will be used to assess the intervention effect. Preliminary data yielded a discordance of 19% between baseline and follow-up measurements. The ORs were 3.4, 2.3, and 2.3 for Harris, Cameron, and NETX, respectively. The OR for the pooled data was 2.55. We use an OR of 2.5 and a discordance of 19%, which represents an 8% difference in the proportion of testing at follow-up compared to baseline, to size the prospective cohort. For a one-sided test at the significance level of 2.5%, a **sample size of 237 is needed to provide 80% power** for confirming the intervention effect. To allow for a **45% loss to follow-up**, 431 participants need to be enrolled at baseline. The table below provides the size options for a one-sided McNemar test of alpha 2.5% and power 80%.

Proportion of discordance	Odds ratio (OR)	Difference in proportion of testing pertaining to OR	Required sample size	Enrollment allows for a 35% loss to follow-up	Enrollment allows for a 45% loss to follow-up
0.19	2	6%	393	605	715
0.19	2.5	8%	237	365	431
0.19	3	9.5%	177	273	322
0.3	1.5	6%	681	1048	1239
0.3	1.727	8%	387	596	704
0.3	2	10%	249	384	453
0.3	2.75	14%	128	197	233

**Statistical Analysis - MC-NET-JITAI.** We will analyze the secondary outcome measures using the McNemar test, conditional logistic regression model, generalized linear mixed model (GLMM). The enrolled individuals completing the follow-up survey constitute the analysis set. In GLMM, we will specify proper random effects to account for hierarchical nesting structure. Secondary analyses will examine the relation between knowledge, attitudes, and intentions on testing and vaccination decisions and we will use the same multilevel GLMM models.

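### Analyses are limited to follow-up completers (237 of 431 at the planned loss), and the promised dropout modelling has no checkable trigger and no named target

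*Combined protocol and SAP*

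**What the plan says.** Under Data Monitoring and Data Management, item 3 (Missing data), the plan states: "The enrolled individuals completing the follow-up survey constitute the analysis set". The sentence appears again after the sample-size table, in the paragraph on secondary outcomes. The rule therefore covers primary and secondary analyses.

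The sample-size section derives 237 completers for 80% power and concludes that "431 participants need to be enrolled at baseline" to absorb a 45% loss. Its table also has a column headed "Enrollment allows for a 35% loss to follow-up".

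Item 3 also says that dropouts and missing-data patterns will be examined and that information on people who drop out will be kept. It notes that traditional regression is valid when data are missing completely at random, but does not claim that this holds here. Dropout modelling is then made conditional: "If the missing data are non-ignorable/informative in the sense that missingness may depend on the missing observations". The method is given only as a general textbook reference: "An attempt will be made to incorporate the missing values mechanism into the model".

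The Statistics section lists the McNemar test, a ratio of odds ratios against the historical controls, and two mixed models. It says nothing about missing outcomes for any of them. General Information and Study Design select the historical controls as people who completed both surveys.

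**The concern.** The objective is the effectiveness of the intervention, and the people offered it are the 431 enrolled. If finishing the follow-up survey is related to testing, the pre-post odds ratio among completers is not the odds ratio among those enrolled. Enrolling 431 to end with 237 protects power. It does nothing for representativeness.

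The plan's safeguard has three gaps:
- **Trigger.** It starts only if missingness depends on the unobserved values. Observed data alone cannot show that, so an analyst has no way to decide whether the step is due.
- **Target.** The model that would carry the dropout mechanism is not identified among the analyses in the Statistics section, and the McNemar test that sizes the study is not a model of that kind.
- **Data.** Modelling dropout needs the records of those who dropped out, but the defined analysis set leaves them out.

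At stake is a report that gives the completers' odds ratio as the intervention effect with up to 45% of outcomes missing and no sensitivity analysis.

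**Working it through.** **1. The plan's own figures.** Inputs from the sample-size section: discordance 0.19, odds ratio 2.5, one-sided alpha 0.025, power 80%. The exact binomial McNemar test, averaged over the number of discordant pairs, has 80.0% power at n = 237. For loss, 237/0.55 = 430.9, so 431. Both figures reproduce.

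**2. How many are left out.** At 45% loss: 431 − 237 = 194, and 194/431 = 45.0%. At 35% loss: 431 × 0.65 = 280, leaving out 151.

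**3. Planned change among completers.**
- Gain = 0.19 × (2.5 − 1)/(2.5 + 1) = 0.0814.
- Not tested to tested: 0.19 × 2.5/3.5 = 0.1357. Tested to not tested: 0.19/3.5 = 0.0543.
- At n = 237 this is 32.2 against 12.9 discordant pairs. Rounded to 32 v 13, the exact one-sided p is 0.0033.

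**4. Gain among all enrolled.** Let g be the change among those lost (assumed; the documents give no data on them). Gain = (n × 0.0814 + lost × g)/431.
- g = 0, 45% loss: 237 × 0.0814/431 = 0.0448.
- g = 0, 35% loss: 280 × 0.0814/431 = 0.0529.
- The gain is zero at g = −237 × 0.0814/194 = −0.099 (45% loss) or −280 × 0.0814/151 = −0.151 (35% loss).

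**5. Would significance be lost at 45% loss?** It depends on convention. Below, e = (237 × 0.0814 + 194g)/431, and discordance among those lost is assumed to be 19% unless stated.
- *Only completer sampling error, g fixed.* The completer standard error is √((0.19 − 0.0814²)/237) = 0.0278, and 237/431 of it is 0.0153. Solving e = 1.96 × 0.0153 gives g = −0.033.
- *Outcomes filled in as if observed.* 37 pairs are added. A 19/18 split gives 51 v 31, p = 0.0176; an 18/19 split gives 50 v 32, p = 0.0299. The tip lies between +0.5 and −0.5 points. At 10% discordance (19 pairs), 9/10 gives p = 0.0164 and 8/11 gives p = 0.0300, so the tip lies between −0.5 and −1.5 points.
- *Imputation variance added.* Variance = (0.19 − e²)/431 + 194(0.19 − g²)/431². At g = +0.01, p = 0.0251; at +0.02, p = 0.0162. Adding (194/431)²(0.19 − g²)/237 for uncertainty in the imputation parameters gives p = 0.028 at +0.02 and 0.019 at +0.03.

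The tip therefore ranges from roughly −3 to +3 points.

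**6. Can those lost move from tested to not tested?** Study Population excludes anyone "having tested for COVID-19 with PCR or antigen test within the past 30 days". The survey table lists the testing items as "Testing for COVID-19, ever tested, last 30 days, positivity, access to testing", and the recall window of the primary outcome is not fixed. If the outcome is the 30-day item, baseline testing should be near zero. If it is the ever-tested item, nobody can revert. In either case every discordant pair among those lost counts upward, the filled-in test can only be stronger than 32 v 13, and the all-enrolled gain is at least 4.5 points.

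**7. Would a missing-at-random adjustment be enough?** Assume follow-up testers are k times as likely to complete. The completers' matched odds ratio is then k times the all-enrolled one, so an observed 2.5 reflects 2.27, 2.0 or 1.67 at k = 1.1, 1.25 or 1.5. Take k = 1.5 and 10% of completers tested at baseline. The completer cells are 0.0457 (both times), 0.1357 (follow-up only), 0.0543 (baseline only) and 0.7643 (neither). Dividing the two follow-up-tester cells by 1.5 gives an all-enrolled baseline testing share of 0.0848/0.9396 = 0.0902. Weighting completers back to that share gives 2.5 × (0.9098/0.90)/(0.0902/0.10) = 2.80. At 6%, 15% and 30% the result is 2.46, 3.01 and 3.22. None recovers 1.67, and three of the four are further from it than the unweighted 2.5.

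**The case against.** A McNemar test needs both measurements, so a completer set is its natural set. That stands, and the test should stay as sized.

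The plan is not silent on dropout. It will examine dropouts, store their information and model informative missingness. That also stands as an intention. What it lacks is a condition anyone can check, a named analysis, and a data set that includes the people concerned.

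The 45% is a planning allowance, not an observed loss. Reminders, a second incentive, and an email or text fallback may bring it down. They do not change what happens to anyone still lost.

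It could also be said that the historical controls, chosen on completion too, cancel the selection when "we will find inferences for the ratio of odds ratios for intervention versus control". For matched odds ratios this is so whenever the ratio of completion rates in the two discordant cells is the same in both groups, even if overall completion differs. The documents do not show whether that holds, and the McNemar test that sizes the study does not use the controls.

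Finally, a tipping-point analysis is one of several acceptable sensitivity analyses, and its absence is not an error in itself. Agreed: the defect is that no analysis of this kind is fixed in advance.

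**Conclusion.** The concern holds as a gap in pre-specification that should be closed. The stated rule leaves out 194 of 431 enrolled people at the planned loss (151 at 35%), and nothing the plan commits to running shows how far the result depends on them. In the illustration the gain falls from 8.1 to 4.5 points (5.3 at 35% loss). This assumes that completers behave as planned and that those lost do not change.

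Three stronger readings are tempting, and the documents do not support them:
- *The completer result is biased upward.* Neither direction nor size can be read from the documents.
- *Significance would vanish if those lost simply did not change.* That is one convention in a range from roughly −3 to +3 points, and it rests on an assumed discordance among those lost. Negative change is ruled out if baseline testing is near zero or the item is ever tested. In that case the planned 5.4% moving from tested to not tested is also in doubt, so the 8.1-point input is itself uncertain.
- *The plan ignores missing data.* It does address it, but not in a form that can be carried out.

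**What to change.** - Keep the completer McNemar test as sized, and define an all-enrolled set (431) beside it.
- Replace the conditional trigger in item 3 with a sensitivity analysis that is always run on the primary pre-post comparison. It should vary the assumed follow-up testing among those lost and report where the conclusion changes. A tipping-point or equivalent pattern-mixture analysis would serve. State the variance method and the range of assumptions in advance.
- Tabulate baseline characteristics of completers and non-completers from part A of the baseline survey, which is completed at enrolment.
- Treat any missing-at-random analysis (mixed model with all baseline records, imputation or weighting) as supplementary. State that it does not correct, and may worsen, bias when completion depends on follow-up testing.

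The cost is SAP wording and some analyst time, since the baseline data are collected anyway. The drawback is that the assumption range is a judgement, and it must be fixed before the data are seen.

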## Statistics

**Statistical Analysis - Main Study Primary Outcomes.** We will conduct a series of analyses regarding the primary outcome variable - testing for COVID-19. First, we will conduct McNemar's test on data from the prospective cohort only. In addition to the test p-value, the odds ratio of COVID-19 testing for post-intervention versus baseline will be evaluated to assess the intervention effect. Second, based on both the prospective cohort and historical controls, we will find inferences for the ratio of odds ratios for intervention versus control. Third, using the prospective cohort, we will build a multi-level generalized linear mixed model (GLMM) including time as a fixed effect factor to evaluate intervention effect. Multiple random effects will be specified to account for the hierarchical structure of persons nested within PBGs nested within regions. Additionally, we will test variables such as individual demographics and baseline measures of rapid testing uses and include significant variables as the fixed effect factors. We will also test the PBG-level of Social Determinants of Health (SDOH) (e.g., % of minority, % of people with no insurance) to investigate the SDOHs as a potential effect modifier on the intervention effectiveness. We will also compute various network measures based on personal networks and organization affiliation patterns associated with COVID-19-related outcomes. Finally, we will build a GLMM to data of both the prospective cohort and historical controls. We will specify proper random effects to account for hierarchical nesting structure.

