## Objectives

The primary objective of this study is to:

- 1) Determine the effectiveness of the adapted MC-NET-JITAI (Multilevel Community network-informed Just-In-Time-Adaptive Intervention) versus a historical control group.

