## Study Design:

**RADx-UP Phases I & II.** (The parent studies) We conducted a three-arm group randomized trial to assess the impact of multilevel interventions influencing motivation and access to testing: Arm 1) Community Engaged Just-In-Time Adaptive Intervention (Community JITAI) where we met regularly with community partners and exchanged community-specific information about COVID-19 (testing, infection rates, etc), Arm 2) Standard multilevel intervention (MLI), and a usual practice condition. We randomized 120 PBGs identified as communities with high levels of disparities across our three geographic regions to each condition using a covariate adaptive Randomization (Minimization) Schedule.

The primary outcome for the Phase I and II studies was community-level SARS-CoV-2 testing (primarily PCR testing). This measure was assessed bi-monthly throughout the study. We also conducted an embedded panel study to 1) compare the effectiveness of the CHW-Facilitated Self-Sampling Intervention (FSSI) vs. CHW Testing Navigation Intervention (TNI). In the ongoing study, we also collected social network data on a sub-sample of individuals to explore the influence of social networks on testing decision-making and behavior.

**RADx-UP Phase III:** Our Phase III study design focuses on **vulnerable communities** selected to intervention and control conditions and takes advantage of the fact that these communities were randomized to conditions using methods to ensure balanced arms. In Phase III, we will combine the two intervention conditions (TNI & FSSI), and will receive the MC-NET-JITAI. The study will include PBGs from each of the two intervention conditions in Phase II; they will be matched to the comparison PBGs on variables such as size, vaccination and testing rates, and the disparities index with the control group. The intervention will last 8 weeks; individuals will be recruited and asked to complete a survey (including RADx-UP common data elements).

In Phase III, we will utilize a historical control group consisting of 400 participants from the control arm who completed the baseline and follow-up surveys in the Phase II embedded study.

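### The comparison with historical controls, which is the primary objective, gives no entry criteria for the controls and names no covariates, so it can be biased by an amount the documents do not let one determine.

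*Combined protocol and SAP*

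**What the plan says.** Under Objectives, the one primary aim is to determine the effectiveness of the intervention "versus a historical control group".

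**Who is compared.** Study Population introduces its criteria with "the inclusion criteria for the enrolled intervention study arm individuals include being aged 18 years to 89 years and having a smartphone" and then excludes, among others, people with a recent COVID-19 diagnosis or a COVID-19 test in the preceding 30 days. Study Design describes the controls as a group "consisting of 400 participants from the control arm who completed the baseline and follow-up surveys in the Phase II embedded study". General Information and Control Arm add nothing on the controls' eligibility or enrolment dates.

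**How they are compared.** Statistics has two analyses that use both groups: "Second, based on both the prospective cohort and historical controls, we will find inferences for the ratio of odds ratios for intervention versus control", and "Finally, we will build a GLMM to data of both the prospective cohort and historical controls". For the second, only random effects are mentioned. The covariate sentence, which would test variables such as "individual demographics and baseline measures of rapid testing uses and include significant variables as the fixed effect factors", belongs to the preceding model, fitted to the prospective cohort alone.

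**Safeguards.** Study Design says that Phase III "takes advantage of the fact that these communities were randomized to conditions using methods to ensure balanced arms", and that intervention block groups will be "matched to the comparison PBGs on variables such as size, vaccination and testing rates, and the disparities index".

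**The concern.** The comparison is not randomised at the level of individuals and is not concurrent. Area-level randomisation and matching do not balance the people recruited or the calendar period. General Information describes systematic sampling with a random start in Phase II and convenience sampling in Phase III, and Background Information itself says that testing, infection and vaccination conditions have shifted markedly.

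A ratio of pre-post odds ratios largely removes stable level differences between groups. It does not remove differential trends, or a baseline lowered in one group by an entry rule. That second problem is specific here, because the exclusion of recent testers is a screen on the primary outcome. If it applied to one group only, the ratio can exceed 1 with no intervention effect, and the primary objective would be answered by an artefact.

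**Working it through.** **1. The plan's own figure.** The Sample Size section uses discordance 0.19, OR 2.5 and one-sided alpha 2.5%. Exact McNemar power at 237 is 0.8001, and 237/0.55 = 430.9, so 431. Both reproduce. They size the within-cohort test, not the comparison with controls.

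**2. Model for the screen (assumptions).** Constant testing rate h; look-back W days; visit at F = 56 days; no intervention effect; testing probability p = 0.10-0.20 per look-back, so h = -ln(1-p)/W; intervention group has no test in the 30 days before enrolment; controls unscreened (pre-post OR 1.0). Group sizes are 237 and 400. Wald test on the log ratio from discordant pairs (0.5 added), one-sided 2.5%, 100,000 simulated trials. The documents give neither W nor p.

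*W = 56.* Baseline can be positive only from the 26 days before the screened period; follow-up covers 56 days after enrolment.
- p = 0.10: baseline 1 - 0.9^(26/56) = 0.0477, follow-up 0.10. OR = (0.10 × 0.9523)/(0.0477 × 0.90) = 2.22.
- p = 0.20: baseline 0.0984. OR = (0.20 × 0.9016)/(0.0984 × 0.80) = 2.29.
- Approximate check at p = 0.10: expected discordant pairs are 22.6 and 10.2 (cohort) and 36 and 36 (controls). SE = √(1/22.6 + 1/10.2 + 2/36) = 0.445. Power = Φ(0.796/0.445 - 1.96) = 0.43; simulation gives 0.42.

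*W = 60.* Baseline 30 usable days, follow-up 56. OR 1.91 (p = 0.10) to 1.96 (p = 0.20).

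*W at least F + 30 (86 days here).* Not tested to tested: (1 - e^(-Fh)) × e^(-(W-30)h). Tested to not tested: (1 - e^(-Fh)) × e^(-(W-30-F)h) × e^(-Fh). These are equal, so OR = 1.00 exactly.

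| Look-back | Ratio | False rejection, ratio | False rejection, cohort-only exact McNemar |
|---|---|---|---|
| 56 days | 2.2-2.3 | 42-72% | about 51-86% |
| 60 days | 1.9-2.0 | 28-54% | about 35-68% |
| 90 or 120 days | 1.0 | about 2% | about 2% |
| 56-90 days, both groups screened | 1.0 | about 2% | as above |

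The boundary moves with the visit. Recruitment allows follow-up from 5 weeks to about 4 months. At 5 weeks the 56-day ratio falls to about 1.4 (8-13% rejection); at day 90 or later the 90-day ratio rises to 1.5-1.6 (16-30%).

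**3. The look-backs named in the survey table** (ever tested; last 30 days). With 30 days, the screened cohort's baseline is about zero, so no pair can move from tested to not tested. Exact McNemar rejects once 6 of 237 report a test (0.5^6 = 0.0156); with 5% testing at follow-up and no effect, that happens 98% of the time. With ever tested, no one can reverse in either group, so the ratio is undefined.

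**4. Planning inputs.** Discordance 0.19 and pooled OR 2.55 imply 0.19/(1 + 2.55) = 0.0535 moving from tested to not tested, or 0.0535 × 237 = 12.7 people. Apart from recall error and tests between screening and survey, that cannot occur in the screened cohort under either named look-back.

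**5. Power of the ratio test at the plan's inputs.** Cohort pairs: 237 × 0.19 = 45.0, split 32.2 and 12.9. Controls (assumed OR 1.0, discordance 19%): 38 and 38. SE = √(1/32.2 + 1/12.9 + 2/38) = 0.402. Power = Φ(0.916/0.402 - 1.96) = 0.63, and 51-69% by simulation for control discordance of 10-30%. A relative calendar drift of 0.8 (apparent OR 2.0) or 0.67 (about 1.68) in the cohort leaves about 33-47% or 21-29%.

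**The case against.** The Phase II protocol is not among these documents and may contain the same exclusion. Study Population may cover only the intervention arm because no controls are being recruited. If both groups had the same screen, the ratio is 1.0 and rejection about 2% (undefined at 30 days). The windows of 56, 60 and 90 days are mine, not the plan's. The design is openly called historical, areas are matched, and Phase II also recruited both door to door and through organisations, so a different recruitment mix is conjecture. All of this stands. It limits what can be said about size, but it does not supply the missing criteria or covariates. A generous reader could carry the covariate sentence to the combined model, but the text does not.

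Two stronger readings are tempting. One is that the cohort-only McNemar test is biased whatever the outcome definition. It is not: under the model above the bias vanishes once the look-back exceeds the visit gap by 30 days. The other is that the planning inputs demonstrate bias. They show only that the preliminary data used another look-back or people not screened this way; their source is not stated.

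**Conclusion.** The omission is certain; the bias is conditional. The controls' eligibility is not stated, and neither two-group analysis names a covariate, although these analyses carry the primary objective. If only the intervention arm was screened on recent testing, look-backs shorter than the visit gap plus 30 days distort both the ratio and the cohort-only McNemar test, and a 30-day look-back makes the pre-post odds ratio uninterpretable. Longer look-backs do not have this problem. The false-rejection rates rest on the assumed constant testing rate, 10-20% testing per look-back, no effect and unscreened controls. A reader might infer that the trial's comparison is biased by a factor of about two; the documents do not support that, because they give neither the look-back nor Phase II eligibility. Calendar confounding is a separate matter: it can act in either direction and remains whatever the look-back.

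**What to change.** 1. State whether the Study Population criteria applied to the controls. Restrict controls to those who meet them as far as Phase II baseline data allow (age, no test or diagnosis in 30 days, smartphone if recorded), as the main or a sensitivity analysis.
2. Fit the combined mixed model with arm, time, arm-by-time and prespecified baseline covariates common to both surveys: demographics, region, vaccination, COVID-19 history, intention, self-efficacy and the block-group disparities index. Do not select them by significance.
3. State the outcome look-back.
   - If it is 30 days, test the primary objective by a covariate-adjusted comparison of follow-up testing in the aligned groups, and do not read the McNemar odds ratio as an intervention effect. In Phase III that window lies after enrolment even at a 5-week visit; Phase II follow-up timing needs checking.
   - For other look-backs shorter than the visit gap plus 30 days, keep arm-by-time in aligned groups and caveat the McNemar result.
   - For longer ones, keep the planned pre-post analyses.
4. Report the comparison as non-randomised and non-concurrent, with residual calendar confounding in either direction.

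**Cost.** Analysis text and work on data already held. If 30-day testing among controls is 10-20% (assumed), 40-80 of 400 are lost, leaving 320-360. The follow-up-only test, where used, gives up the removal of stable differences: a residual level odds ratio of 1.25 would by itself give 13-20% false rejection. Its power for the plan's 8-point difference, at 10-20% control testing and before clustering, is 0.62-0.78 with 400 controls and 0.59-0.76 with 320, so below 80%. It also needs step 1: with unscreened controls its odds ratio under no effect would be 0.66-0.95, assuming testing rates that vary between people (gamma variance 0.5-2).
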